# **Device Training and System Configuration**

Prior to the enrollment of the first subject, the study sponsor (Analog Devices) will train the study team on the proper setup, fitting, placement, and use of the CPM System. The CPM System Web App will also be configured such that there is a separate user "bucket" specifically for each cohort of this clinical study to ensure data privacy and organization.

The reference device will also be configured as necessary to maintain traceability and facilitate data management and analytics. Study site staff will be trained on the proper configuration, application, and use of the reference and safety devices as per their associated Instructions for Use as they pertain to the metrics required to fulfil the study objectives.

# Subject Identification, Recruitment and Informed Consent:

Screening of participants will take place based on the inclusion/exclusion criteria. For the pathologic cohort, this will be based initially on a review of the individual's medical records. If an individual meets all the inclusion/exclusion criteria of either cohort then the investigator or designated study coordinator will approach the potential participant to discuss the details of the clinical study, including the risks and benefits of participating in the research study. Eligible healthy participants will be identified by the PI and research team using the criteria specified in this protocol, initially from [name] laboratory database of potential participants. Pathologic participants can be identified either while they are admitted in the hospital, or when they return to Mayo Clinic for a scheduled physical or follow up visit, or from [name] laboratory database of research participants who are diagnosed with cardiopulmonary disorders. IRB approved letters, flyers, and postings on the Mayo website may also be used in recruitment for both cohorts.

Enrollment in this study is completely voluntary. At the time of recruitment, participants will be introduced to the study by the research team verbally and in writing. If the participant expresses interest, written consent will be obtained and documented at the time of the discussion by the IRB approved consent designees. Participant information and informed consent will be presented detailing the exact nature of the study as well as any risks involved in taking part. It will be clearly stated that the participant is free to withdraw from the study at any time for any reason without prejudice to future care, and with no obligation to give the reason for withdrawal. The participant will be allowed as much time as they wish to consider the information and the opportunity to

question the Investigator, their GP or other independent parties to decide whether they will participate in the study.

Participants who have verbally consented will be asked to complete the informed consent form and return it to the clinical staff before the start of the study. Participants will be provided a copy of the informed consent for their records. Pathologic patients will also be asked to complete the HIPAA Authorization to Use and Disclose Protected Health Information. No patient data will be collected prior to this. Once the form has been signed, the study can begin.

Written consent will be obtained, documented, and maintained as part of the research records. No identifiable patient information will be maintained, other than a randomly assigned subject number and patient ID that is generated by the CPM System.

## **Pre-Screening:**

Before signing the Informed Consent form, subject will be screened by the study team for eligibility based on the inclusion and exclusion criteria.

## **Baseline Evaluation:**

The following evaluations are required at the time of subject enrollment:

- 1. Medical history and current status skin disorders;
- 2. Medical history and current status allergies;
- 3. Medical history and current status electronic implants;
- 4. Medical history and current status cardiopulmonary disorders or illnesses including date of onset, recent hospitalizations and/or treatments, and medications taken;
- 5. Evaluation of device application site for broken, damaged, or irritated skin or rashes;
- 6. Demographics information: Age, Gender, Height, Weight

These assessments will be recorded in the CRF. Subjects who meet all inclusion and none of the exclusion criteria for either of the cohorts will then be able to proceed with the study and will be considered enrolled once measurement capability of the device on the subject has been verified.

## **Risks and Benefits:**

Participating in this study poses minimal risk to participants. The ADI CPM Device is a non-significant risk, noninvasive medical monitoring device. The device is IEC 60601 compliant and meets all standards needed for FDA approval. There is slight risk that the adhesive used on both the reference and test devices will cause mild skin irritation due to prolonged adhesion of the devices as well as hair in the area. If this is case, the participant can decide to stop the study at any time. Hair in this area may also have to be trimmed if initial data collection proves to be a challenge. This will be done by the study team.

This laboratory has used all the listed reference devices for numerous studies, and there are no excessive risks of using these devices.

Finally, there is a slight possibility that performing the breathing exercises outlined in this protocol for the healthy cohort will cause participants to experience shortness of breath, dizziness, or syncope. An SpO2

monitor will be used as a backup safety mechanism in addition to constant supervision of study activities by the study team and the study will be paused if any of these symptoms are noted.

There is always a risk for disclosure of electronic data. The data collected from the devices will be stored on an internal secure server and secure cloud platform. If transport of electronic data is necessary for any reason an encrypted storage device will be used. The research team will be responsible for any data entry. Access to the data will be restricted to only research personnel approved on the IRB application, and the study sponsor. The research team will complete the institution's IRB education requirements for staff assisting with research data. Additionally, the devices used in the study store no identifiable patient information other than Patient ID and upload data to the cloud securely. Smartphones used in the study as well as the cloud repository are password protected and store Patient ID with no patient identifiable information. In other words, all patient data will undergo HIPAA-compliant de-identification.

By taking part in this study, participants will have a chance to aid in the validation of this novel device that will eventually have an impact on those living with cardiopulmonary disease.

## Setting:

All study activities will take place at the Mayo Clinic in Rochester, MN in [name] laboratory.

## **Study Procedures:**

#### Healthy Cohort

Patients will be recruited and begin the study as they are identified and consent to the study. Recruiting will end when 20 patients have initiated the study. One participant will participate in the study at a time, with the duration of the single study visit lasting approximately two hours (the total commitment for any given participant being approximately half a day at the most).

Upon arrival to the clinic on the day of the study visit, prior to the application of the reference and test devices, skin inspection of the application site will be conducted. The CPM Device will then be applied to the participant's chest as described in the IFU materials supplied with the device (the study team will also have received training on the proper placement of the device prior to the initiation of the study). This device will be worn for the entirety of the clinic visit (without removal and replacement). The reference device will also be used for each measurement taken during the visit, concurrently. On the CRF, the time that the CPM Device is placed on the chest will be denoted.

A Baseline measurement will then be initiated using the CPM Mobile Application in order to assign a systemgenerated patient ID to the participant as well as to establish the tilt angle for the following measurements. The first half of the measurement should be in the Fowler, sitting-upright position, and the second position should be in a Supine, lying-flat position. The reference device will also be used during this time to establish a respiration baseline.

The exercises below will then be followed, with the time of the start of each exercise recorded in the CRF. Each exercise will last approximately 2 minutes, or the time that it takes to complete one full measurement with the CPM device in measurement mode (initiated by the CPM mobile app). Within each measurement, participants will move through two positions, both Fowler and Supine. Reference respiration data will be taken concurrently with the CPM device measurement.

Item	Respiration Rate	Tidal Volume	Mode	Duration
1	Natural (baseline)	Natural (baseline)	Doctor Setup, App	3 min
2	6 BPM	Natural	Patient, App	2 min
3	10 BPM	Natural	Patient, App	2 min
4	15 BPM	Natural	Patient, App	2 min
5	20 BPM	Natural	Patient, App	2 min
6	25 BPM	Natural	Patient, App	2 min
7	30 BPM	Natural	Patient, App	2 min
8	35 BPM	Natural	Patient, App	2 min
9	40 BPM	Natural	Patient, App	2 min
10	15 BPM	Natural (~500mL peak-to-peak)	Patient, App	2 min
11	15 BPM	Shallow breaths (< 500mL p2p)	Patient, App	2 min
12	15 BPM	Deep breaths (> 500 mL p2p)	Patient, App	2 min
13	10 BPM	Extremely deep "yoga" breaths (> 750 mL p2p)	Patient, App	2 min

A single metered breathing app or metronome will be used to pace respiration rates throughout the study. The same breathing measurement method will be used across all patients. It is assumed that actual respiration rates will differ slightly from those described in the protocol. Higher and lower respiration rates may be tailored slightly to accommodate the abilities of participants. During both phases of varying respiration rate (items 1-9 in above table) and varying tidal volume (items 10-13 in above table), both respiration rate and tidal volume will be tracked from the reference device.

Readings will not be considered "successful" or "complete" unless all CPM device errors are resolved prior to the device streaming mode. In the case that a contact or tilt error cannot be resolved, the measurement must be repeated until the data quality is deemed sufficient. If the device begins peeling off of the skin during a measurement (as noted by a participant) and the streaming data quality looks questionable, the measurement must be repeated and the adhesives replaced to ensure good contact. The IFU can be followed for troubleshooting tips regarding issues with data quality. The device may have to be replaced, the skin moisturized, or the adhesive on the device replaced. Any note regarding measurement issues and steps taken to resolve these issues must be noted in the CRF.

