## **Endpoints**:

- Respiration Rate RMSE < 2 BPM between reference and test device at 8-40 BPM
- Relative Tidal Volume Precision has an  $R^2$  value > 0.5

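### The healthy-cohort tidal-volume exercises run in one fixed order, so steady signal drift is confounded with breath depth; counterbalancing them would be a cheap safeguard

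*Combined protocol and SAP*

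**What the plan says.** Study Procedures, Healthy Cohort, gives a single numbered exercise table and one instruction for all subjects: "The exercises below will then be followed, with the time of the start of each exercise recorded in the CRF". Items 1-9 vary the rate at natural volume. Items 10-13 vary the depth:

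- item 10, 15 BPM: "Natural (~500mL peak-to-peak"
- item 11, 15 BPM: "Shallow breaths (< 500mL p2p"
- item 12, 15 BPM: "Deep breaths (> 500 mL p2p"
- item 13, 10 BPM: extremely deep, above 750 mL

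On wear, the same section states: "This device will be worn for the entirety of the clinic visit (without removal and replacement". During both phases "both respiration rate and tidal volume will be tracked from the reference device".

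The derivation section says the CPM measure of relative tidal volume (rTV) comes from breath-driven changes in impedance. Outcome Measures asks for a within-subject correlation, averaged across subjects for immediate and long timeframes; neither timeframe is mapped to exercise items. The healthy-cohort Endpoints entry beginning "Relative Tidal Volume Precision has an" sets R² above 0.5, and its justification equates this with R above 0.7. The analysis text does not say which items enter R² and has no term for order or elapsed time. No text in the available copy randomises or counterbalances the exercises.

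**The concern.** From item 11 onward, depth rises with time on the skin, and only the step from item 10 to item 11 goes the other way. If the breath-driven amplitude rises steadily during the block for any reason other than volume, the within-subject correlation is inflated; if it falls, the correlation is deflated. Because all subjects share the order, the bias has the same sign in each of them and does not shrink with sample size. The result at stake is a primary one, in a study meant to support a 510(k) submission, and the order cannot be changed once the data are collected.

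**Working it through.** **The plan's own figure.** The only healthy-cohort calculation is the sample size: n = ((1.96 + 1.65) × 0.10 / 0.10)² = 13.03, which reproduces the stated 13 (20 planned). It does not depend on exercise order, so it neither helps nor hurts here.

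**Inputs.** From the plan: the order of items, the volume bands, R² > 0.5 (r > √0.5 = 0.707), 20 subjects. Assumed, because the plan gives only bands: 500, 350, 700 and 1000 mL for items 10-13. The plan gives no drift or noise figure for the volume signal, so a range is shown.

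**1. Pure upward drift, items 10-13 only.** Let the signal equal the item position (1 to 4), with no volume response.
- Position deviations: −1.5, −0.5, 0.5, 1.5; Sxx = 5.
- Volume deviations from the mean of 637.5: −137.5, −287.5, 62.5, 362.5; Syy = 236,875.
- Sxy = 206.25 + 143.75 + 31.25 + 543.75 = 925.
- r = 925 / √(5 × 236,875) = 0.85; R² = 0.72.

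Other assumed sets give 0.69 (500/450/550/800), 0.70 (500/400/600/900) and 0.735 (500/300/800/1200). Over a wider grid (item 11 at 150-450, item 12 at 600-1500, item 13 at 800-2500 mL, item 13 deeper than item 12), R² runs from 0.41 to 0.88 and exceeds 0.5 in 99.5% of combinations. Without the last condition it exceeds 0.5 in 92%.

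**2. The same drift over all 13 items**, with items 1-9 at 500 mL (assumed).
- Sxx = 182.
- Sxy = 500 × (−18) + 3×500 + 4×350 + 5×700 + 6×1000 = 3,400.
- Syy = 4,112,500 − 7,050²/13 = 289,231.
- R² = 3,400² / (182 × 289,231) = 0.22, which fails. Over the grid the range is 0.02 to 0.38, never above 0.5.

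**3. Drift plus noise, no volume response, items 10-13.** Share of simulated 20-subject studies with mean r above 0.707:

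| Drift per item (noise SD) | 500/350/700/1000, volume SD 10% | 500/300/800/1200, volumes fixed |
|---|---|---|
| 2 | 99% | 100% |
| 1.5 | 90% | 97% |
| 1 | 31% | 46% |
| 0.75 | 6% | not run |
| 0.5 | 0.1% | 0.3% |

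The chance of a pass falls away steeply; it does not scale in proportion to the drift.

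**4. A borderline device.** Assume a true volume response of 0.75 noise SD per SD of volume, with 500/350/700/1000 mL and volume SD 10%.
- No drift: mean r 0.64; about 19% of studies pass.
- Upward drift of 0.25 noise SD per item: mean r 0.75 and about 75% pass in the fixed order; about 18% pass if randomised.
- Upward drift of 0.5 SD: about 97% pass in the fixed order; about 4% if randomised.
- Downward drift of 0.5 SD, fixed order: mean r 0.28.

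These percentages move by several points with how the volume spread is defined; the contrast between fixed and randomised order does not go away.

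**5. After the change.** With drift alone and the order randomised per subject, mean signed r is 0, with a 95% range for the 20-subject mean of about −0.25 to 0.25. With half the subjects in the listed order and half in reverse, the two r values are 0.85 and −0.85 and average 0. Unsigned R² would not show this: it stays at 0.72 in each subject under listed/reverse, and averages 0.33 under random order.

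**The case against.** A reader might infer that a CPM signal that merely drifts with wear time would meet the rTV limit. The documents do not support that, for these reasons.

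- It requires R² to be confined to items 10-13. The plan names no item set, and reference volume is recorded in items 1-9 too; on all 13 items drift alone fails.
- It requires the breath-driven amplitude itself to rise by roughly 1 to 1.5 noise SD or more per two-minute item. Drift in baseline impedance would not be enough. No passage reports such a rise.
- The text on peeling, moisturising and replacing adhesives describes corrective steps and repeat measurements. These would interrupt a drift; they are not evidence of an upward one.
- For a device that tracks volume well, drift matters little: with noiseless tracking, an upward gain drift of 5% or 10% per item leaves R² at 0.99.

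It would also be too strong to say that volume and wear time cannot be separated. Items 4 and 10 are both 15 BPM at natural volume and lie six positions apart, so a linear drift would be twice as large between them as across items 10-13 (three steps). Start times are recorded as well.

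All of this stands, and it limits the size of the point. It does not remove the shared order. No comparison of items 4 and 10 is planned. Adjusting for position afterwards is possible but costly: with r = 0.85 between position and depth, the variance inflation is 1 / (1 − 0.72), about 3.6, on four points per subject.

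**Conclusion.** The point holds as a conditional design weakness. As written, depth and time on the skin are largely collinear, in the same direction in all 20 healthy subjects, and averaging does not help. If the endpoint uses items 10-13 alone, pure upward drift gives R² of about 0.7; whether noisy data would pass depends almost entirely on the drift-to-noise ratio, which the plan does not supply. The realistic consequence is that a borderline device could be pushed over or under the limit. A false pass has not been demonstrated.

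Confidence is moderate. The volumes, drift and noise are assumptions. The section headed Healthy Cohort Study Activities carries no text in the available copy and some pages are absent, so an order rule placed there cannot be excluded.

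**What to change.** 1. Study Procedures, Healthy Cohort: counterbalance items 10-13 across subjects (for example, half in the listed order and half in reverse) or randomise them from a pre-printed list, subject to the investigator's view of tolerability. Record the order used in the CRF.
2. Healthy Cohort Data Analysis, Effectiveness and Endpoint Analyses: state which items enter the rTV endpoint, and define it as a signed within-subject r averaged across subjects.
3. In the same place, include item position as a sensitivity term, and prespecify a comparison of items 4 and 10, relative to their reference volumes, as a drift check.

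Cost: a sequence list, one CRF field and a few lines of analysis text. There are no added measurements; the 13 items still take 3 + 12 × 2 = 27 minutes of a visit of about two hours. The downside is that staff must follow different sequences for different subjects, with some risk of a sequence error. If the order is kept fixed, steps 2 and 3 are still worth making.

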## Pathologic Cohort

Patients will be recruited and begin the study as they are identified and consent to the study. Recruiting will end when 20 patients have initiated the study. One participant will participate in the study at a time, with the duration of each of two visits lasting approximately one hour (the total commitment for any given participant being approximately 2 hours spread over the course of one day).

Upon arrival to the clinic on the day of the study visit, prior to the application of the reference and test devices, skin inspection of the application site will be conducted. The reference bioimpedance device will be placed on the participant and a reference measurement will be taken. These electrodes will be worn for the entire duration of the study, even between visits, in order to ensure placement consistency, although reference and test impedance measurements will never be taken concurrently and reference measurements will never be taken with the CPM Device on the participant to avoid device interference. The reference bioimpedance device

electrodes will be placed within 2 cm from the CPM Device's electrode placement on the left chest of the participant. After disconnecting the reference device from the electrodes, the CPM Device will then be applied to the participant's chest as described in the IFU materials supplied with the device (the study team will also have received training on the proper placement of the device prior to the initiation of the study). A skin marker will be used to mark around the device in order to later place it in the exact same location. On the CRF, the time that the CPM Device is placed on the chest for the first time will be denoted.

A Baseline measurement will then be taken using the CPM Mobile Application in order to assign a systemgenerated patient ID to the participant as well as to establish the tilt angle for the following measurements. The measurement should proceed with two positions; the first half of the measurement should be in a sitting-upright "Fowler" position, and the second half should be in a lying-flat "Supine" position.

In reference to the table below, subjects will be instrumented with the ADI device and laboratory-based reference impedance device along with a mouthpiece connected to a pneumotachometer and gas analyzer (only for the last three measurement items). In addition, they will be instrumented with an ECG for the indicated items.

The exercises below will then be followed, with the time of the start of each exercise recorded in the CRF. Each exercise will last approximately 2 minutes, or the time that it takes to complete one full measurement with the CPM device in measurement mode (initiated by the CPM mobile app). Reference bioimpedance will be denoted at the beginning of each measurement in both a sitting and laying down position, following the CPM Device measurement flow. All CPM Device measurements include both a Fowler and a Supine portion.

Participants will be asked to breathe normally throughout the course of all measurements, including during the final three measurements which include the use of a device that tracks respiration rate and tidal volume. Reference devices to measure skin temperature and ECG will also be used during clinic visit two, before and after the CPM Device usage.

Subjects are to be instrumented with both the ADI device and reference impedance, mouthpiece, pneumotach, sampling line for O2 and CO2, ECG, and skin temperature.

Item	Description	Device/Mode	Duration	
1	Baseline reference TI measurement*	Bioimpedance reference	1 min	
2	Baseline measurement	CPM/Baseline Setup, App	3 min	
3	Reference TI measurement	Bioimpedance reference	1 min	
4	Application 1/Measurement 1**	CPM/Patient, App	2 min	
5	Application 1/Measurement 2	CPM/Patient, App	2 min	
6	Application 1/Measurement 3	CPM/Patient, App	2 min	
7	Reference TI measurement	Bioimpedance reference	1 min	
8	Application 2/Measurement 1	CPM/Patient, App	2 min	
9	Application 2/Measurement 2	CPM/Patient, App	2 min	
10	Application 2/Measurement 3	CPM/Patient, App	2 min	
t = 1 hour				
11	Reference skin temperature, ECG data	Reference temperature, ECG devices	1 min	

12	Reference TI measurement	Bioimpedance Reference	1 min
13	Application 3/Measurement 1; RR/TV	Reference spirometer, CPM/Patient,	2 min
	measurement	Арр	
14	Application 3/Measurement 2; RR/TV	Reference spirometer, CPM/Patient,	2 min
	measurement	Арр	
15	Application 3/Measurement 3; RR/TV	Reference spirometer, CPM/Patient,	2 min
	measurement	Арр	
16	Reference skin temperature, ECG data	Reference temperature, ECG devices	1 min

\* Measurements with the bioimpedance reference device refer to the length of time that it takes to get a stable thoracic impedance reading in both a sitting and lying down position.

\*\*Measurements with the CPM Device refer to one entire reading of the CPM System, which takes approximately 2 to 3 minutes and includes both sitting and lying down in each measurement.

Readings will not be considered "successful" or "complete" unless all CPM device errors are resolved prior to the device streaming mode. In the case that a contact or tilt error cannot be resolved, the measurement must be repeated until the data quality is deemed sufficient. If the device begins peeling away from the skin during a measurement (as noted by a participant) and the streaming data quality looks questionable, the measurement must be repeated. The IFU can be followed for troubleshooting tips regarding issue with data quality. The device may have to be replaced, the skin moisturized, or the adhesive on the device replaced. Adhesives will be replaced between each placement of the test device. Any note regarding measurement issues and steps taken to resolve these issues must be noted in the CRF.

